10.1 Sample Size

We have powered our study on the basis of superiority of valproate compared to placebo on the PANSS positive subscale using an effect size of 0.3. An effect size of 0.3 was selected as, in line with other trials of antipsychotic augmentation for treatment resistant schizophrenia, effects smaller than this are considered unlikely to be clinically meaningful [51, 52]. Assuming a two-sided significance level of 0.05 and 1:1 allocation, we will require 290 participants in the analysis dataset to detect an effect size of 0.3 with 90% power. This allows for a correlation between measures (at baseline and three follow-up points) of 0.4. An estimate of attrition of 20% across both arms for the primary end-point at 12 months requires a recruitment total of 362 participants at

baseline. The attrition rate of 20% is an estimate based on studies of antipsychotic augmentation using a similar design to our proposal, for example, the FOCUS study (Cognitive therapy augmentation of an antipsychotic for treatment resistance) had an attrition rate of ~10% over 21months [53] and the CHAT study (antipsychotic augmentation with a second antipsychotic) had an attrition rate <10% [54]. In this context, a study of a novel drug as an augmentation agent to antipsychotic treatment had a discontinuation rate of 29% at 12 months [55]. This study had a considerably larger burden of measures and higher levels of monitoring than our study. As such we expect our attrition and discontinuation rates to be in the range of 10-20% level in line with the other studies.

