Purpose of clinical trial	To assess the efficacy and cost-effectiveness of valproate when used to augment antipsychotic treatment in patients with schizophrenia or schizoaffective disorder whose illness shows inadequate response to first-line antipsychotics
Primary outcome	The PANSS positive (psychotic) score at the end of the double-blind study (12 months)
Secondary outcomes	The main secondary outcome will be PANSS positive score difference at 3 months
	Additional secondary outcomes include: - PANSS positive score at 6 months - Change in PANSS factor scores at 3, 6- and 12-

month follow-up visits

- Total PANSS scores at 3, 6- and 12-month follow-up visits
- Change in other clinical measures at 3, 6 and 12-month follow-up visits
- Patient reported outcome (well-being) at the
 3, 6 and 12-month follow-up visits
- Cost effectiveness assessment using measures collected at baseline, 3, 6 and 12month follow-up visits
- Adverse effects at baseline, 3, 6-month and
 12-month follow-up visits
- Discontinuation of the medication at 3, 6 and 12-month follow-up visits
- Long-term symptomatic and functional outcomes using the HoNOS in an annual fashion during the extension phase till the end of the trial
- starting clozapine treatment

Trial Design

This is a two-arm parallel group randomised 12-month placebo-controlled double-blind trial. Following baseline measures, patients will be randomly assigned 1:1 to either valproate + antipsychotic or placebo + antipsychotic arms.

Sodium valproate will be started at a daily dose of 500mg PO and titrated between 500 mg/day to 2500 mg/day of valproate (depending on body weight) over two weeks. The placebo will be titrated in the same way.

After the end of one year, each patient in both arms will be down titrated and valproate/placebo augmentation will be stopped over a two-week period.

After the 12-month follow up visit, patients will be followed up using electronic databases to capture long-term clinical and functional outcomes using the Health of the Nation Outcome Scale (HoNOS) till the end of the trial.

Sample Size	362 patients

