4.1.1 Primary outcome

• Superiority of valproate compared to placebo on the Positive and Negative Syndrome Scale (PANSS) positive subscale at the 12-month visit [4].

The primary outcome is the positive subscale of the PANSS, which measures psychotic symptom severity. The PANSS is a clinician-rated scale that assesses psychotic (positive), negative and general symptom severity in schizophrenia. The PANSS psychotic (positive) rating at the end of the double-blind study (12 months) will serve as the main outcome measure [4]. The positive scale has seven items covering psychotic symptoms (delusions, conceptual disorganization, hallucinations, excitement, grandiosity, suspiciousness/persecution and hostility), each rated from 1 (absent) to 7 (very severe). The scale's reliability, criterion-related validity, and construct validity have been well documented [29].

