Flow Diagram Patients to be assessed post consent (N = 460)Diagnosis of schizophrenia and schizoaffective (DSM-5) Inadequate response to first line antipsychotics Fail to meet inclusion criteria (symptom severity, comorbid conditions, past medication adherence history, clinical safety criteria) Withdrawal of consent Baseline assessment (N = 362) Including PANSS '+'ive score Randomization 1:1 allocation (Time point 0) Placebo + current antipsychotic (N = 181) Valproate + current antipsychotic (N = 181) 3 and 6 month follow up 3 and 6 month follow up Primary outcome (PANSS '+'ive score) Primary outcome (PANSS '+'ive score) Secondary outcomes Secondary outcomes Double blind phase Pharmacoeconomic measures Pharmacoeconomic measures One year follow up (N = ~145) One year follow up $(N = \sim 145)$ Outcomes similar to earlier time point Outcomes similar to earlier time point Attrition 10-20% from baseline Attrition 10-20% from baseline Mainly due to withdrawal of consent Mainly due to withdrawal of consent Post-one year follow up Post-one year follow up Annual electronic records Annual electronic records HoNOS database HoNOS database Electronic patient journey records Electronic patient journey records

Attrition rate of 30% at the randomization step and 20% from allocation based on two similar augmentation studies – Morrison et al, Lancet Psychiatry, 2018. Vol 5:p663 and Cipriani et al, J Clin Psychopharmacology, 2013. Vol 33(4):p533.

DSM-5 - Diagnostic and Statistical Manual of Mental Disorders, Fifth Edition (Standard manual for psychiatric diagnosis); PANSS - Positive and Negative Syndrome Scale (Clinical scale for evaluating severity of schizophrenia); HoNOS - Health of the Nation Outcome Scales (a measure of the health and social functioning in psychiatric patients captured yearly by mental health care teams)

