10.3 Analysis

Statistical analysis will be done according to the predefined statistical analytical plan (SAP). There is no planned interim analysis unless the DMEC direct us to conduct one. Any deviations will be reviewed by the trial steering committee.

Statistical analysis

The primary analysis will use intention-to-treat principles by including all participants with outcome data in the arms to which they were randomized and follow the CONSORT 2010 statement. Baseline data will be presented using summary statistics with no testing for baseline differences. Treatment effects on the primary and secondary continuous outcomes will be estimated using linear mixed models fitted to outcome variables at all-time points. Fixed effects will be: diagnosis (schizophrenia/ schizoaffective); centre; baseline PANSS psychotic symptom severity rating; treatment; time (categorical); and time*treatment interactions. Marginal treatment effects will be estimated for outcomes at each time point and reported separately as adjusted mean differences in scores between the randomised groups with 95% confidence intervals and two-sided p-values. For binary outcomes, the same approach will be followed using logistic mixed models. All models will be estimated using maximum likelihood estimation, which allows for missing outcome data under the Missing At Random assumption. We may also use inverse probability weighting or multiple imputation to adjust for non-adherence to allocated treatment and other intermediate outcomes as predictors of future loss to follow-up.

Secondary analysis will include accounting for treatment switches from placebo to valproate arms using inverse probability of censoring weighting to estimate the average

treatment effect and longitudinal instrumental variable analysis to estimate the complier average causal effect.

Cost effectiveness evaluation

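### The stated 90% power for effect size 0.3 does not hold for the 12-month primary outcome: 290 analysed at correlation 0.4 give about 80%

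*Protocol*

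**What the plan says.** Section 10.1 sets the inputs: "Assuming a two-sided significance level of 0.05 and 1:1 allocation", then "we will require 290 participants in the analysis dataset to detect an effect size of 0.3 with 90% power". It adds: "This allows for a correlation between measures (at baseline and three follow-up points) of 0.4". Recruitment is raised to 362 for "An estimate of attrition of 20% across both arms for the primary end-point at 12 months", and the section expects attrition to fall between 10% and 20%. The synopsis repeats the calculation. The Rationale repeats 90% power, effect size 0.3, 20% attrition and 362 patients.

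Section 4.1.1 fixes the target: "Superiority of valproate compared to placebo on the Positive and Negative Syndrome Scale (PANSS) positive subscale at the 12-month visit". Section 4.1.2 makes the 3-month and 6-month PANSS positive scores secondary. Section 10.3 plans a linear mixed model with baseline PANSS severity, categorical time and time-by-treatment terms, and states: "Marginal treatment effects will be estimated for outcomes at each time point and reported separately". Nothing in the protocol makes an average over visits the primary estimand.

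The flow diagram in section 4.2 shows 460 assessed after consent and 362 at baseline, with the note: "Attrition rate of 30% at the randomization step and 20% from allocation based on two similar augmentation studies".

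**The concern.** The sample-size text takes credit for a correlation across four measurements, but the primary comparison uses one follow-up visit. Repeated follow-ups save many patients when the outcome is their average. They save almost none when each visit has its own treatment effect and only the 12-month effect is primary. Without baseline adjustment, 90% power for 0.3 at a single visit needs 468 patients, so 290 implies a much larger saving than correlation 0.4 can give.

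The figure matters because the Rationale calls 0.3 the smallest clinically significant effect and says that a null result could spare the NHS about £60 million a year of ineffective valproate. At an effect of exactly 0.3, the stated chance of missing it is 10%. If power is about 80%, that chance is about 20%.

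**Working it through.** **Inputs.** From section 10.1: two-sided alpha 0.05, 1:1 allocation, effect size d = 0.3, correlation 0.4, 290 analysed (145 per arm), 362 randomised, attrition 20% with 10–20% expected. From sections 4.1.1 and 10.3: 12-month outcome, baseline-adjusted, with a separate effect per visit. Assumptions: d is in units of the between-patient SD of the score, and the correlation is 0.4 between every pair of measures.

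**Formulas.** With variance factor f:
- n per arm = 2(1.960 + 1.282)² / 0.3² × f = 233.5 × f
- power at n per arm = Φ(d / √(2f/n) − 1.960)

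**Reproducing 290.** The protocol names no formula. These are the standard two-sided variants at correlation 0.4:

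| Contrast | f | N for 90% | Power at 290 |
|---|---|---|---|
| 12 months, unadjusted | 1.00 | 468 | 72.4% |
| 12 months, baseline-adjusted | 0.84 | 394 | 79.6% |
| 12 months, change score | 1.20 | 562 | 64.5% |
| Mean of 3 follow-ups, unadjusted | 0.60 | 282 | 91.0% |
| Mean of 3, baseline-adjusted | 0.44 | 206 | 97.1% |
| Mean of 3, change score | 0.80 | 374 | 81.5% |

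Only the unadjusted mean of three follow-ups comes close to 290. The attrition step is consistent: 290 / 0.8 = 362.5.

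**The planned 12-month contrast.**
- f = 1 − 0.4² = 0.84.
- Standard error = √(2 × 0.84 / 145) = 0.1076.
- Power = Φ(0.3 / 0.1076 − 1.960) = 79.6% (79.3% with the t distribution).
- For 90%: 233.5 × 0.84 = 196.1, so 197 per arm or 394 analysed. Randomised at 20% attrition: 394 / 0.8 = 492.5, so 493.
- For 80%: 294 analysed.
- Effect detectable with 90% power at 290: 3.242 × 0.1076 = 0.349.
- Correlation needed for 90% at 290: √(1 − 145/233.5) = 0.62.

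**What the earlier visits add.** With complete data and a separate effect per visit, they add nothing to the 12-month contrast. With 362 randomised and 290 seen at 12 months, the mixed model gives 80.6% if every dropout has 3- and 6-month data, and 80.2% if dropout is gradual.

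**Attrition.** At 10%, 326 are analysed (163 per arm) and power is Φ(0.3 / √(1.68/163) − 1.960) = 84%. With all 362 seen it is 87.6%.

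**Which SD scales 0.3.** At 290 analysed:
- SD of change: d becomes 0.3 × √(2 × 0.6) = 0.329, and power is 86.3%.
- Residual SD: this is equivalent to f = 1, and power is 72.4%.

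**Flow diagram.** 1 − 362/460 = 21.3%. A 30% loss from 460 would leave 322; reaching 362 after a 30% loss would need 362 / 0.7 = 517.1, about 518 consented.

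**The case against.** The strongest reply is that 80% is itself conditional. The protocol gives no SD, and section 4.2 describes the primary measure as change in the PANSS positive subscale, so 0.3 may be scaled by the SD of change. Section 10.1 also expects attrition as low as 10%. This stands as a reason to give a range and name the SD. Taking both favourable readings together, 326 analysed and d = 0.329 give Φ(0.329 / 0.1015 − 1.960), about 90%. But the protocol claims 90% at 290 analysed, where even the change-SD reading gives 86%.

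It is also fair that a null result will be judged by its 95% confidence interval, not by design-stage power. At 145 per arm the half-width is 1.96 × √(1.68/145) = 0.21 SD, so an estimate near zero would still exclude 0.3. The shortfall raises the risk of an inconclusive result; it does not by itself rule out the use the Rationale makes of a null finding.

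Three stronger readings are tempting but unsupported:
- **That the trial was powered for the average over visits.** The nearest formula gives 282, not 290, and the protocol names none, so the origin of 290 remains an inference.
- **That the 90% could be kept by attaching it to the averaged effect.** The planned model adjusts for baseline and would give about 97% for that average. The 91% belongs to an unadjusted analysis that is not planned.
- **That the flow diagram implies only 322 randomised and power of about 75%.** Section 10.1 sets 362 as the recruitment total, and section 6.3 allows sites to be added if recruitment falls short. Nothing stops consenting at 460.

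**Conclusion.** The power statement is wrong as written. For the protocol's own 12-month, baseline-adjusted, visit-specific contrast, 290 analysed at correlation 0.4 give about 80% power for effect size 0.3, against the stated 90%. This assumes that 0.3 is scaled by the between-patient SD of the score. Under the other two scalings, power at 290 runs from 72% to 86%. That no scaling considered reaches 90% at 290 is firm; the exact size of the shortfall depends on an SD that the protocol does not name. The 21% against 30% mismatch in the flow diagram is a minor inconsistency about screening numbers and has no bearing on power.

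**What to change.** Keep N = 362. In the synopsis, the Rationale and section 10.1:
- State which SD standardises 0.3.
- If it is the SD of the score, restate power for the 12-month contrast at correlation 0.4 as about 80% for 0.30 (90% for about 0.35) at 20% attrition, and about 84% for 0.30 at 10% attrition. If it is another SD, give the matching figure: at 290 analysed, about 86% for the SD of change or 72% for the residual SD.
- Do not move the 90% to the effect averaged over visits.

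Separately, reconcile the flow diagram: either a loss of about 21% from 460, or about 518 consented at a 30% loss.

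The cost is wording only. No patients are added and the analysis does not change; the stated power becomes less favourable.

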10.2 Randomisation

Randomization will be stratified by diagnosis (schizophrenia or schizoaffective), site and sex and a permuted block randomization will be used for each stratum.

10.3 Analysis

Statistical analysis will be done according to the predefined statistical analytical plan (SAP). There is no planned interim analysis unless the DMEC direct us to conduct one. Any deviations will be reviewed by the trial steering committee.

Statistical analysis

The primary analysis will use intention-to-treat principles by including all participants with outcome data in the arms to which they were randomized and follow the CONSORT 2010 statement. Baseline data will be presented using summary statistics with no testing for baseline differences. Treatment effects on the primary and secondary continuous outcomes will be estimated using linear mixed models fitted to outcome variables at all-time points. Fixed effects will be: diagnosis (schizophrenia/ schizoaffective); centre; baseline PANSS psychotic symptom severity rating; treatment; time (categorical); and time*treatment interactions. Marginal treatment effects will be estimated for outcomes at each time point and reported separately as adjusted mean differences in scores between the randomised groups with 95% confidence intervals and two-sided p-values. For binary outcomes, the same approach will be followed using logistic mixed models. All models will be estimated using maximum likelihood estimation, which allows for missing outcome data under the Missing At Random assumption. We may also use inverse probability weighting or multiple imputation to adjust for non-adherence to allocated treatment and other intermediate outcomes as predictors of future loss to follow-up.

Secondary analysis will include accounting for treatment switches from placebo to valproate arms using inverse probability of censoring weighting to estimate the average

treatment effect and longitudinal instrumental variable analysis to estimate the complier average causal effect.

Cost effectiveness evaluation

Costs will be captured from two perspectives: NHS & personal social services (PSS) and a wider societal perspective that will include criminal justice services, caregiver out-ofpocket expenses and lost productivity. The client service receipt inventory (CSRI) adapted for use in this study will be used to collect service use and support data for each participant in the study that will be used to generate cost from these two perspectives [36]. The CSRI facilitates the standardised recording of service use that is commensurate with accurate cost estimation. Through a patient interview, data on service use and caregiver support will be collected for the 3-month period prior to assessment at baseline (for the period prior to entering the study), and at 6 and 1-year follow-up interviews. During the treatment period, we use data collected on the treatment dosages and titration schedules. Also at baseline, 3-month 6-month and 1year, the SF-36 (36-item short form health survey) will be transformed into a single preference-based measure of health using the algorithm developed by Brazier and colleagues [46]. Using the area under the curve method with linear interpolation between assessment points (and baseline adjustment for comparisons), the qualityadjusted life-year (QALY) gain for each patient will be generated.

From each perspective, in turn, the cost-effectiveness evaluation will compare the comprehensively measured service and support costs between the placebo plus continuing antipsychotic treatment arm and the valproate plus continuing antipsychotic treatment arm with, first, the difference between the treatments in the primary outcome measure (psychotic symptom severity as measured by the PANSS positive subscale), and then with the difference between the treatments in QALYs gained. In each case, an incremental cost-effectiveness ratio (ICER) will be computed as the mean cost difference between placebo plus continuing antipsychotic treatment arm and the valproate plus continuing antipsychotic treatment arm divided by the mean difference in change in primary and secondary outcome respectively. The cost-effectiveness measures will be incremental cost per point improvement in PANSS positive subscale (by 3, 6 month and 1-year) and incremental cost per QALY gain by 12 months. We will use the current standard NICE cost-effectiveness threshold range of £20K and £30K per OALY to determine if the intervention meets cost-effectiveness criteria.

For the base-case models under both perspectives, we will compare costs and outcomes between the treatment arms at baseline, 3-month, 6- month and 12-months follow-up. In these models we will control for baseline costs (only in the cost analysis); centre; baseline PANSS psychotic symptom severity rating; treatment; time (categorical); and time*treatment interactions.

Bootstrapping with mixed effects models will be used to generate confidence intervals that can be used to capture parameter uncertainty around the estimates in the cost-

effectiveness analysis. The 1000 treatment effect replications from this bootstrapping process will be plotted on cost-effectiveness planes and used to construct cost-effectiveness acceptability curves (CEAC). We will use cost effectiveness acceptability curves (CEACs) to explore the nature of the trade-off faced by the decision-maker in situations where one treatment option is both more effective and costly than the other. In this case, the decision maker would need to consider if it is worth incurring the higher costs to improve outcomes. Using this approach, we will be able to show the likelihood of valproate plus continuing antipsychotic treatment arm being seen as cost-effective relative to the placebo plus continuing antipsychotic treatment arm given different (implicit monetary) values placed on incremental outcome improvements. Bootstrapping and regression analysis will be used to generate CEACs. We will also explore the sensitivity of the results to changes in key parameters and the analyses will be repeated. This will include the same control variables as those in the base-case model.

11 Trial Steering Committee

The Trial Steering Committee (TSC) will be constituted in accordance with the NIHR HTA programme guidance before the start of the trial. The TSC chair will be an experienced independent member and the majority of the TSC members (75%) will be independent of the trial. At least one individual who can contribute as a patient or carer perspective will be included. In the initial stage of the trial (first six months) the TSC will review progress with respect to trial recruitment and retention and recommend changes if needed to the protocol and conduct of the trial. Thereafter it will be convened periodically at least once a year to monitor progress. The TSC will provide overall supervision of the trial and monitor trial progress and conduct and advise on scientific credibility. In the event of serious adverse events, or on the advice of the Data Monitoring and Ethics Committee, the TSC will direct action to be undertaken to ensure safety of the participants and will review trial continuation.

12 Data Monitoring Committee

A Data Monitoring and Ethics Committee (DMEC) will be constituted in accordance with the NIHR HTA programme guidance before the start of the trial. It will be the only independent body involved in the trial that will have access to the unblinded comparative data. An independent clinician in the relevant area and an expert trial statistician will be part of the committee. It will meet initially six months after the trial start and then at least once a year to monitor trial data and make recommendations to the TSC with regards to 1) recruitment of patients, 2) ethical issues in the overall conduct of the trial, 3) quality of data (including missing data), 4) incidence of adverse events and 5) any factors that may compromise the progress and satisfactory completion of the trial. The pharmacokinetic and pharmacodynamic interaction between antipsychotics and sodium valproate will be specifically monitored during the trial.

13 Patient and Carer involvement

The study protocol was developed in active consultation with carers and patients at service user meeting at SLAM. Service user and carer groups at each site and an overall study patient and carer advisory board will advise us on national and local implementation of the study and would guide us in our recruitment strategy. They will also provide feedback on issues that arise as the study progresses (including the ICF) and help us write study outcome documents. Feedback from local groups via the patient and carer advisory board will be provided to the Trial management group (TMG) and they will disseminate information to all sites and implementation of actionable items will be decided by the TMG. The TMG will also disseminate information arising from the consultation to the TSG and Data Monitoring and Ethics Committee (DMEC) if needed.

14 Direct Access to Source Data and Documents

The Investigators will permit trial-related monitoring, audits, REC review, and regulatory inspections by providing the Sponsors, Regulators and REC direct access to source data and other documents (e.g. patients' case sheets, clinical test reports, etc.).

15 Ethics & Regulatory Approvals

The trial will be conducted in compliance with the principles of the Declaration of Helsinki (1996), the principles of GCP and in accordance with all applicable regulatory requirements including but not limited to the Research Governance Framework and the Medicines for Human Use (Clinical Trial) Regulations 2004, as amended in 2006 and any subsequent amendments.

This protocol and related documents are reviewed by the UK's Health Research Authority's Research Ethics Committee (REC), and the Medicines and Healthcare products Regulatory Agency (MHRA) for Clinical Trial Authorisation. Subsequent amendments will be submitted to the REC and regulatory authorities for approval. We will also comply with the pharmacovigilance requirements under the Medicines for Human Use (Clinical Trial) Regulations 2004 (as amended).

The Chief Investigator will submit annual progress reports and a final report at conclusion of the trial to the KHP-CTO (on behalf of the Sponsor), the REC and the MHRA.

All revisions and/or amendments (substantial or non-substantial) to this protocol must be approved in writing by the sponsor, the REC, the HRA and MHRA (if applicable). Emergency deviations or modifications may be initiated with sponsor, the REC, HRA or MHRA approval or favourable opinion, only in cases where the deviation or modification is necessary to eliminate or avoid an immediate apparent hazard to subjects. Emergency

deviations will be reported to the sponsor, REC, HRA and MHRA within five business days.

16 Quality Assurance

KHP-CTO will undertake, on behalf of the Sponsor, independent administrative audits of the trial master file and monitoring at all sites and pharmacies periodically during the trial to ensure compliance with the Medicines for Human Use (Clinical Trials) Regulations 2006 and its subsequent amendments.

17 Data Handling

The Chief Investigator will act as custodian for the trial data. The following guidelines will be strictly adhered to:

Patient data will be anonymised.

- All anonymised data will be stored on a password protected computer.
- All trial data will be stored in line with the Medicines for Human Use (Clinical Trials) Amended Regulations 2006 and the Data Protection Act and archived in line with the Medicines for Human Use (Clinical Trials) Amended Regulations 2006 as defined in the Kings Health Partners Clinical Trials Office Archiving SOP.

18 Data Management

Paper case report forms will be completed at sites. Data will be transferred to an electronic data management system (Infermed MACRO ver 4). The system is compliant with Good Clinical Practice and is an appropriate system to use for medicinal trials falling under the Medicines for Human Use (Clinical Trials) Regulations 2004 and its subsequent amendments. The web-based system will be available for access 24 hours a day. Roles will be assigned to users, giving the ability to enter data relating to participants or to view data and raise discrepancies, but not amend data. Roles will also be tailored to be blind to treatment allocation where appropriate. The system is programmed to perform validation checks, such as range checks to prevent data entry errors. Missing data codes are routinely programmed into all fields, for ease of analysis. The system is also programmed to flag up when a missing data code is entered, to aid monitoring. The system is also programmed to include e-signatures, where this is required. A standard feature of InferMed MACRO data entry system is the built-in audit trail on all data fields, the automatic saving of data as you leave a form, and the ability to maintain a record of 'source data verification' checks. The system also has formal database lock functionality.

The investigator at each study centre will arrange for retention of study records for at least 10 years from time of participation in the study. Precautions to prevent accidental destruction must be taken. All data storage will adhere to General Data Protection Act (GDPR) Act 2018.

19 Publication Policy

The trial protocol will be published in a peer-reviewed open access journal. The results of the study will be disseminated at national and international conferences and submitted for publication in peer-reviewed open access scientific journals. Authorship will be granted to individuals making significant contribution to the design, setup or conduct of the trial and/or analysis and interpretation of trial data. The study findings will also be disseminated to patients and carers through presentations at local service user research networks and through national patient newsletters.

20 Insurance / Indemnity

